research outreach programs. I have budgeted in salary support for a research coordinator two days per week throughout Years 1-4 of the award. The research coordinator will screen all interested participants by phone to assess study eligibility, explain the purpose of the study and study procedures, and answer any questions. For individuals interested and eligible in participating, youth will complete the informed assent process and their parent/guardian will complete the informed consent process (detailed below). In addition to the phone screening of eligibility criteria, an in-person eligibility assessment will be conducted with the PI and research coordinator to assess for DSM/SIPS diagnostic criteria, explain the study procedures in more detail, and answer any questions. Recruitment will be done until there are enough participants to randomize and fill two groups of $n > 6$ per group.

Overview of study activities: Aim 1 will consist of focus groups, followed by an iterative app-development process with an interdisciplinary expert panel, and then an open trial of an app-enhanced cognitive-behavioral treatment (CBT). Focus groups will be held in a conference room at the UCLA Semel Institute and last approximately 60 minutes. The open trial will consist of a pre-treatment assessment, nine 90-minute group treatment sessions, and post-treatment session that includes an exit interview. Aims 2 & 3 will consist of a RCT of the app-enhanced CBT, which will compare nine 90-minutes sessions of the group CBT to nine 90-minute sessions of the app-enhanced group CBT. The RCT will also consist of a pre-treatment assessment, a post-treatment assessment, and a 3-month follow-up assessment following the completion of the group. The open trial and the RCT will be held in group therapy rooms at the UCLA Semel Institute. Finally, I will conduct longitudinal and machine learning analyses of data collected throughout the RCT.

Study Procedures, Materials, and Potential Risks

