Data Monitoring

Study recruitment, enrollment, and retention will be reviewed by the PI and research coordinator weekly and by the primary mentor ([name]) and co-mentors (Drs. [name] and [name]) monthly. Additionally, twice annually, the scientific advisory committee consisting of the PI, his mentors, and the collaborator and consultants (Drs. [name], [name], and [name]) will review study recruitment, enrollment, and retention at one of the regularly planned meetings with this team. Informed consents and randomization will also be reviewed weekly by the PI and study coordinator and monthly by the PI's mentors for the purposes of quality control. The research coordinator will report any difficulties in recruitment, enrollment, mobile application (app) implementation (e.g., technological bugs), or other study related difficulties during weekly team meetings.

The focus groups, open trial, and RCT involve data collection via clinician-rated interview/assessment, participant self-report on the mobile app, and speech samples collected via a voicemail-like voice journal. All participant data will be kept confidential and accessible only to approved study staff. Clinician-rated interviews/assessments will not contain any personally identifying information and will be secured in a locked cabinet in the PI's office. Participants' self-report data and speech samples will be collected using the Chorus Innovative Platform and stored on its server, a secure and encrypted server housed within UCLA that has been approved by the university's IRB to house personal health information on multiple research projects within the hospital. These data will only be accessible to study staff approved by the UCLA IRB. The clinical psychology postdoc will review the data collected on the mobile app and the speech samples daily and report any clinically concerning information (e.g., suicidal ideation/intent) immediately to the PI. The PI will then consult with the mentorship team and take any needed action in accordance with California state law and best clinical practice (see Protection of Human Subjects). The PI and his mentors will serve as the data safety and monitoring board to review study participant safety, study progress, and study-related events (including adverse events). As needed, an action plan will be established to ensure continued progress and success in both study and training goals.

Vulnerable Subjects

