session. Suicidal ideation may also emerge from the participant's weekly responses to the mobile app, which contain questionnaires about mood and suicidality. Independent evaluators will contact the study PI if there is an increase in suicidal ideation or self-harming behavior so that crisis counseling can be introduced or emergency services can be commenced. When a participant endorses suicidal thoughts, the clinician will conduct a thorough lethality and safety assessment and arrange hospitalization if necessary.

If the suicide risk is deemed low, the project clinician will intervene to prevent deterioration. Prevention will include additional meetings with the participant following each treatment sessions. These meetings will involve some or all of the following: (a) conducting chain analyses to assess the precipitants and consequences of suicidal thoughts or actions, (b) developing a suicide prevention contract (i.e., identifying triggers for suicidal thoughts; clarifying the steps by which parents can get in touch with the psychiatrist or therapist and what to do if they are unavailable), (c) enhancing family members' expressions of support, concern, and compassion; and (d) family problem-solving to eliminate triggers of the proband's suicidal thoughts and prevent their worsening.

Availability of Other Ancillary Treatments

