Participants may require out-of-protocol emergency services such as hospitalization or other psychosocial programs. These participants will be retained in the protocol whenever possible. A participant who needs to be hospitalized (e.g., for suicidality) will be reentered into the protocol after hospital discharge if the participant and family agree to continue. Participants will not be withdrawn if they seek ancillary psychosocial treatments outside of the study. We recognize that the availability of adjunctive non-protocol treatments could statistically confound our results, especially if they occur in one treatment condition more than another. This potential threat to internal validity must be balanced against the clinical needs of the adolescent participant, which may not be met by study protocol interventions. As indicated, we will record each participant's non-protocol treatments (e.g., medications received, frequency and type of extra psychotherapy sessions) using a *Treatment Utilization Form*. We will examine in the data analyses whether the adolescents in the two treatment conditions differ in the intensity (e.g., number of non-protocol sessions), costs, or duration of ancillary services or crisis sessions. We will then use these variables as covariates when evaluating the effects of treatment condition on the teen's symptomatic, functional, or family outcome variables. In the primary mentor's prior studies in mood disorders (e.g., [name] et al., 2013), youth at high-risk for bipolar disorder in FFT and Enhanced Care did not differ on the frequency of variables such as undertaking ancillary therapies, emergency room visits, school counseling, or hospitalizations.

Circumstances That May Require Study Withdrawal

Noncompliance. Participants will be withdrawn from the protocol if they are noncompliant with the study procedures (for example, miss 4 consecutive treatment sessions without calling ahead; refuse to participate in follow-up interviews). The circumstances that may require administrative withdrawal will be spelled out in the consent forms.

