The benefits to participants are moderate to high. Participants will have the opportunity to discuss ongoing concerns related to their psychiatric symptoms, including difficulties managing their mood and unusual experiences. Specifically, participants in the groups will have the opportunity to discuss experiences that other peers may not relate to and may even stigmatize. Discussing these experiences and concerns within a group setting provides youth with valuable peer support. This shared experience can help foster self-acceptance, self-efficacy, and emotional validation. Participants engaging in the open trial or the RCT will also be learning evidence-based cognitive-behavioral skills that have been shown to be efficacious for similarly aged youth. Thus, getting exposure to these skills can provide the participants with useful methods of managing stress and coping with their psychiatric symptoms. Additionally, the participants who receive the app-enhanced treatment will have the luxury of readily-accessible psychoeducation and CBT skills on their smartphone. Quick and easy access to psychoeducation and therapeutic skills provides these participants with a beneficial resource that is not commonly available.

Any potential risks to participants, which we believe are minimal, are reasonable and outweighed by these moderate to high potential benefits.

IMPORTANCE OF THE KNOWLEDGE TO BE GAINED

Knowledge Gained

The scientific significant of this study is detailed in the Research Strategy. SMD affects a significant proportion of the population, creating a significant emotional and financial burden on society. Finding ways to intervene effectively in the early stages of SMD is critical. While there are current interventions for the early stages of SMD (most notably CBT), their efficacy is inconsistent and with small effect sizes overall. One proposed reason for the small effect sizes is the low rates of patient compliance to treatment. CBT, as a skills-based

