The power calculation assumes a two-sided significance level, $\alpha=.05$, and a within-subject correlation of $r=.5$ between repeated measures. Under these calculations, for outcomes measures at the three primary assessment time-points, we have 80% power to detect an overall group by time interaction corresponding to a differential treatment effect across the two study arms with an effect size of $f=.30$, just above the above Cohen's threshold for a medium effect ($f=.25$). Thus, recruiting 60 participants will provide ample data for this pilot RCT in order for us to determine initial clinical meaningfulness for the larger grant application to follow this study. However, in accordance with NIMH guidance on the role of pilot RCTs (see: <https://grants.nih.gov/grants/guide/rfa-files/RFA-MH-18-706.html>), this study does not propose to formally assess clinical efficacy or estimates of effect size, due to the unreliability of estimates and limited statistical power yielded from pilot studies.

Statistical analyses

Aim 1 – App acceptability:

- Open trial acceptability: Following the open-trial, we will score participants' rating of app acceptability and treatment satisfaction and burden. We expect high ratings of acceptability (scores>4/5) for the treatment and the app. We will also calculate participant adherence via the extent of weekly practice and percentage of weekly skills practiced. We expect the percentage of weekly skills practiced to be greater than our pilot study as well as the average homework adherence in the literature (>50%).

Aim 2 – Pilot RCT of App-UP:

- Primary Analyses: Treatment conditions will be compared using a general linear mixed modeling (GLMM) approach for the weekly measurements of treatment adherence (both self-report and clinician rated measures) using IBM SPSS software. Time will be based on the standard interval assessments of the study – the baseline, post-treatment, and follow-up assessment). Time, treatment condition, and their interaction will be the primary predictors (controlling for any significant covariates).

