 1. Using functional data analytic techniques, the uptake of that app will be examined. First, each of the components of participant adherence (skill-practice, symptom monitoring, and review of session content) will be examined to determine the functional pattern of participant adherence over time. This analysis will examine the trajectories of each component of participant adherence over the study to examine their function (i.e., increasing, decreasing, stable over time). Additionally, this analysis will determine which component of participant adherence had the highest frequency of practice.
 2. The frequency and duration of app use will be mapped across the study to determine how often and for how long participants engaged with the app. Additionally, the frequency and duration of app use will be moderated with time of reward reinforcement to determine if the use of the app was affected by the reward structures (e.g., leveling up, receipt of an emoji) within the app.

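### The app is the randomised difference and also the named route for weekly self-report, and the plan gives controls no equivalent route, so recorded adherence may differ by arm because of how it is captured

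*Combined protocol and SAP*

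**What the plan says.** All references are to the combined protocol and SAP.

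- **Randomised contrast.** The overview of study activities says the RCT will "compare nine 90-minutes sessions of the group CBT to nine 90-minute sessions of the app-enhanced group CBT". The app is the only stated difference between the arms. The section on benefits to participants says that "the participants who receive the app-enhanced treatment will have the luxury of readily-accessible psychoeducation and CBT skills on their smartphone", which points to the app arm alone.
- **Route of self-report.** Data Monitoring describes data collection for the focus groups, open trial and RCT together. Beside clinician-rated interviews it names "participant self-report on the mobile app, and speech samples collected via a voicemail-like voice journal". It makes no distinction by arm.
- **Eligibility.** Inclusion criterion 5 asks for a smartphone for use with the study app. It covers the open trial and the whole RCT.
- **Number of measurements.** Power calculations expects app data to add greatly to the number of measurements, again without naming an arm.
- **Primary analysis.** Under Aim 2, the arms are compared by mixed model on "the weekly measurements of treatment adherence (both self-report and clinician rated measures"). The secondary analyses use average adherence over the study as the mediator between arm and clinical outcome.
- **Adherence components.** The exploratory analyses examine "each of the components of participant adherence (skill-practice, symptom monitoring, and review of session content").
- **Other adherence measures.** Two compliance scales are collected at post-treatment, and maintenance of adherence at the 3-month follow-up. App usability is in the same list of measures on which the treatments are to be compared.

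**The concern.** A fair comparison of adherence needs the same measuring instrument in both arms. Here the named instrument for self-report is also the treatment under test. According to the Knowledge Gained section, the app reminds participants to practise, supplies the practice material and rewards its use.

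If controls do not have the app, their weekly practice must be reported some other way, and arm and recording method then coincide. Prompted reporting close to the event may catch practice that later recall misses, which would favour the app. Recall may also overstate practice, which would count against it. The documents do not settle the direction.

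If controls do report on the app, they use at least its monitoring function, and symptom monitoring is itself counted as adherence. That would shrink the difference between arms.

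Because adherence is both the primary outcome and the mediator, a recording difference would enter the mediation analysis as well.

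**Working it through.** **Step 1: do the sections settle what controls do?**

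| Section | Points towards |
|---|---|
| Overview of study activities; benefits to participants | App in one arm only |
| Data Monitoring; Addressing Clinical Emergencies (weekly app questionnaires described under precautions for all participants) | App reporting, no arm named |
| Inclusion criterion 5 | Neutral: applied before randomisation, so it must cover everyone |
| Aim 2 list of measures compared between treatments, including app usability | App use in both arms, or a measure with no evident meaning for controls |
| Data collection, management, and protection; Protections Against Risk | A web form on the Chorus data platform is possible, but none is planned |

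No row states the instrument, mode or frequency of weekly self-report for controls.

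**Step 2: inputs for an illustration.** The plan has no figure for a recording effect, so there is none to reproduce. Its power statement concerns a group-by-time interaction and is not used here.

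- From Power calculations: 60 randomised 1:1 and 15-20% dropout. 60 × 0.85 = 51 and 60 × 0.80 = 48, which agrees with the stated figure of about 50, or 25 per arm. Two-sided alpha is .05.
- Assumed, because the documents give nothing: the recording route alone shifts measured weekly practice by 5, 10 or 15 percentage points, with SD 25. So d = 5/25 = 0.2, 10/25 = 0.4, 15/25 = 0.6.

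**Step 3: recording shift with no true difference.** Two-sample t test with n = 25 per arm, df = 48 and critical value 2.011. The noncentrality is d × √(n/2) = d × √12.5 = d × 3.536.

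| Assumed shift d | Noncentrality | Chance of p < .05 |
|---|---|---|
| 0 | 0 | 5.0% |
| 0.2 | 0.707 | 10.7% |
| 0.4 | 1.414 | 28.3% |
| 0.6 | 2.121 | 54.7% |

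**Step 4: the opposite direction.** Suppose a true difference of 0.6 SD (assumed). A shift of 0.2 SD against the app leaves a net 0.4, and power falls from 54.7% to 28.3%. A shift of 0.4 SD leaves a net 0.2, and power falls to 10.7%.

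**Step 5: dilution.** Suppose the same true 0.6 SD, and that controls gain a fraction c of the app's effect. The net difference is 0.6 × (1 − c).

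| c | Net d | Power |
|---|---|---|
| 0 | 0.60 | 54.7% |
| 25% | 0.45 | 34.5% |
| 50% | 0.30 | 18.0% |
| 75% | 0.15 | 8.1% |

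These are single-comparison figures, not results for the planned mixed model on repeated measures.

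**The case against.** The strongest reply is that this is a gap in description and not a demonstrated flaw. Several parts of that reply stand.

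- **A neutral form is not excluded.** Chorus is described as a web-based data tool as well as an app platform, and survey responses are to be entered into it. An identical measurement-only form in both arms would avoid both problems. A reader might infer that the plan fails whichever way controls report. The documents do not support that, because the two alternatives are drawn partly from silence. But no section plans such a form either.
- **The Data Monitoring sentence pools study components.** It also covers focus groups that precede the app, so it cannot by itself prove control-arm app use. It does name the RCT, and nothing else supplies a control route.
- **There are other adherence measures.** Clinician ratings belong to the primary analysis and are not said to be collected on the app, and the compliance scales follow at post-treatment. A reader might infer that nothing could separate a recording artefact from a real effect. That goes too far: disagreement between these measures and self-report would be informative, though not conclusive. The plan does not say what information the clinician raters use.
- **Suicidality.** A reader might infer that it is measured differently by arm. The documents provide for inquiry at every study assessment and at the check-out of every session, in both arms. The app is supplementary: "Suicidal ideation may also emerge from the participant's weekly responses to the mobile app, which contain questionnaires about mood and suicidality". Suicidality is not named as an outcome in the analysis section. What remains is narrower. It is unclear whether the weekly app responses and their daily review apply to both arms, and the section on ancillary treatments compares the arms on the intensity, costs or "duration of ancillary services or crisis sessions" and then uses these variables as covariates.
- **Documents not supplied.** The protocol refers to a Recruitment and Retention Plan and a Research Strategy. The mode by arm may be stated there.

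**Conclusion.** The concern holds as a weakness of the plan as written. Taken literally, the app is both the randomised difference and the stated channel for self-report, and self-report is part of the primary weekly measure. Differential recording of the primary outcome, or control exposure to part of the app, therefore cannot be excluded. The first could bias the comparison in either direction; the second would dilute it and would not imitate a benefit.

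The size is unknown. The 10.7% to 54.7% range shows only how sensitive a comparison with 25 per arm would be to shifts of 0.2 to 0.6 SD. It rests on assumed shifts and a single t test, and is not an estimate for this trial. That the plan is a pilot and disclaims formal efficacy testing lowers the stakes for clinical outcomes, but adherence is its primary comparison and is meant to inform the larger trial. It should be settled before randomisation, since a common measure cannot be added after the data are collected.

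**What to change.** 1. State the instrument, mode and schedule of weekly adherence self-report for each arm.
2. Use one identical measurement-only form in both arms, with the same wording and timing. It could be a Chorus web form without therapeutic content, prompts or rewards, or a form completed at each group session. Any effect of answering the form is then shared by both arms.
3. Base the between-arm primary and mediation analyses on that form and the clinician ratings.
4. Restrict app-logged data to the exploratory analyses of app use in the app arm, and report any app exposure among controls.
5. Say whether app usability is rated in the app arm only. If so, remove it from the between-arm comparisons.
6. Reconcile Data Monitoring with Addressing Clinical Emergencies on whether the weekly app mood and suicidality responses, and their daily review, apply to both arms.

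The cost is a short form on a platform the trial already uses and a few minutes per participant per week. The drawback is that app-arm youths may answer some items twice.

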This study proposes to recruit a relatively young (ages 13-17) sample. If the researchers have reasonable cause to believe that child abuse or neglect is occurring, or there are circumstances which might result in child abuse or neglect, they will comply with California state laws by filing a child abuse report with the Department of Child and Family Services. If the research staff believe that a participant is at risk of harming someone else, they are required to take necessary actions. These actions include notifying the parent of the participant's intentions, notifying others who might be affected (i.e., intended victims), or notifying the police or the Department of Child Services. In these cases, the research staff will be unable to preserve the participant's confidentiality. These limits to confidentiality will be spelled out in the participants' consent and assent forms. We will notify parents if we learn that an adolescent participant is actively abusing alcohol or drugs in a way that is life-threatening or otherwise a danger to him- or herself or others. If an adolescent participant has experimented with a drug or alcohol on a single occasion, notifying the parents may not be indicated. Nonetheless, it will be necessary to monitor this behavior in family or individual support sessions. If we disclose these behaviors to parents, we will meet with the family to help resolve family conflicts and introduce preventative measures. Additional counseling sessions beyond the required number will be tabulated and included as covariates in the treatment/outcome analyses.

Protections Against Risk

Data safety will be maintained to the most rigorous standards as detailed above. Survey responses will be entered into Chorus. Electronic and audio data will be stored within the UCLA Health System's encrypted firewall, will be password protected, and protected by anti-virus software. Any hard copies of participants' data will only contain a unique study ID and stored in a locked filing cabinet within the PI's office. All study codes (including a link between participant names and identifying information) will be kept in a password-protected electronic file on a secure server. Password access will be limited to the PI and to any individuals that are IRB

approved for this study. All study links between participant IDs, names, and identifying information will be destroyed when the study has ended. Approval of all study documents will go through UCLA's IRB.

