Significant symptomatic or functional deterioration. If a participant or family member endorses significant symptomatic or functional deterioration at any point throughout the study protocol or if study staff witness significant deterioration, the participant will be encouraged to seek services with ancillary psychosocial and/or psychopharmacological therapy. Study staff will make every effort to continue to include the participant in the study protocol and participants will be continued in the treatment if they continue to consent to treatment, can tolerate the study protocol, and are not a disturbance to the group setting of the treatment. In cases where the patient requires hospitalization, can no longer tolerate the study protocol, or become a disturbance to the group, the participant will be withdrawn from the study.

Participants will have been informed of these rules during the recruitment phase of the study, both through information given orally and via our informed consent procedures. We will make clear that discontinuing participation in the study will in no way jeopardize their access to other treatments provided by outpatient or inpatient services at the study site. Whenever possible, we will continue to follow these adolescents/YAs using the research outcome battery so that they can be included in intent-to-treat analyses.

Reporting Adverse Events

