The remaining measures for treatment adherence (i.e., Homework Compliance Scale and Psychosocial Compliance Scale), as well as measures for app acceptability (i.e., Subjective App Usability Scale) and treatment acceptability (i.e., Subjective Treatment Acceptability) will be collected at the post-treatment assessment. Maintenance of treatment adherence will also be collected at the 3-month follow-up assessment. Treatments will be compared on these outcome measures using one-way analysis of variance (ANOVA).

- **Secondary analyses:** Treatment conditions will be compared using a general linear mixed modeling (GLMM) approach for secondary outcome variables (i.e., psychiatric functioning and psychosocial functioning) using IBM SPSS software. Time will be based on the standard interval assessments of the study – the baseline, post-treatment, and follow-up assessment). Time, treatment condition, and their interaction will be the primary predictors (controlling for any significant covariates). Psychiatric symptoms, psychosocial functioning, and emotion regulation (measured continuously) will be the outcome variables for these analyses.

We will also test a mediation analysis, with average participant adherence (measured throughout the study) as the mediator between treatment conditions and the secondary outcome variables. This will be done in two sets of analyses using the SPSS Process macros, which is a statistical package within SPSS that runs bootstrapped mediation analyses. First, the effect of treatment condition, mediated by average treatment adherence, on post-treatment psychiatric and psychosocial functioning will be examined. Second, the effect of treatment condition, mediated by average treatment adherence, on 3-month follow-up psychiatric and psychosocial functioning will be examined.

- **Exploratory analyses:** Two exploratory analyses will be examined. We will make use of the app's big data collection to begin to elucidate the app's effect on participant adherence and clinical outcomes.

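### Outcome models are to be adjusted for counseling, crisis and ancillary services received after randomisation, which can distort the effect of assignment, mainly on symptoms and functioning

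*Combined protocol and SAP*

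**What the plan says.** Under Availability of Other Ancillary Treatments, the protocol will compare the arms on the intensity, costs or duration of ancillary services and crisis sessions. It continues: "We will then use these variables as covariates when evaluating the effects of treatment condition" on symptomatic, functional or family outcomes. Its reason is "We recognize that the availability of adjunctive non-protocol treatments could statistically confound our results".

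Limits to Confidentiality adds a second rule: "Additional counseling sessions beyond the required number will be tabulated and included as covariates in the treatment/outcome analyses".

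Two other sections show when such services arise. Addressing Clinical Emergencies, for suicide risk judged low, states: "Prevention will include additional meetings with the participant following each treatment sessions". Circumstances That May Require Study Withdrawal, on significant deterioration, states that "the participant will be encouraged to seek services with ancillary psychosocial and/or psychopharmacological therapy".

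Statistical analyses uses the same sentence for the primary (adherence) and secondary (symptoms, functioning) mixed models: "Time, treatment condition, and their interaction will be the primary predictors (controlling for any significant covariates"). It does not limit covariates to baseline, name a services covariate, or call any adjusted model a sensitivity analysis.

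**The concern.** Randomisation balances the arms, in expectation, on everything that precedes it. A service received later cannot be a common cause of assignment and outcome, so it is not a confounder. If the arms differ in service use, the difference is either a consequence of assignment or chance.

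Ancillary and crisis services are also partly a consequence of the outcome, because worse mood or suicidality brings more of them. Holding them constant then removes part of the effect being estimated. If the app reduces the need for services, adjustment can understate a real benefit. If the app arm only receives more services, for instance because app entries are reviewed daily (plausible, but the documents do not show that this differs by arm), adjustment can create a benefit that does not exist.

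The rule on ancillary treatments reaches symptom, functional and family outcomes. The counseling rule names no outcome, so together with the open-ended covariate clause it could extend to adherence, the primary outcome.

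**Working it through.** The plan gives no figure to reproduce and no service-use rates, so every size below is an illustration. Negative values are benefit.

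**1. The mechanism.** In a linear model at one visit,

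adjusted effect = unadjusted effect - β × D,

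where β is the within-arm slope of outcome on services and D is the arm difference in mean services. If D = 0 the expected shift is zero. Otherwise its sign depends on β and D.

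**2. Inputs.** From Power calculations: within-subject correlation r = .5, three visits, about 50 completers (25 per arm). Assumed: services in each post-baseline interval S = ρY + √(1-ρ²)u + δT, with Y and u of unit variance, T the arm and ρ = .3/.5/.6. Case A has a true effect τ = -0.40 SD at both later visits and δ = 0. Case B has τ = 0 and δ = 0.3 SD more services in the app arm.

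**3. Single-visit model.** Here β = ρ and D = ρτ + δ, so the adjusted effect is τ(1-ρ²) - ρδ.
- Case A: -0.40 × (.91/.75/.64) = -0.364/-0.300/-0.256, an attenuation of 9%/25%/36%.
- Case B: -ρ × 0.3 = -0.09/-0.15/-0.18.

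**4. Three-visit mixed model** with time, arm and arm × time (simulated with complete data, 400,000 participants per cell). The plan does not say how services enter. Shifts are adjusted minus unadjusted, in SD; the interaction is the mean of the two later visits.

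| Services entered as | Quantity | Case A, ρ=.3/.5/.6 | Case B, ρ=.3/.5/.6 |
|---|---|---|---|
| One total per person | interaction | 0/0/0 | 0/0/0 |
| One total per person | condition effect averaged over visits | +.047/+.117/+.165 | not run |
| Per interval | interaction | +.025/+.070/+.108 (6%/18%/27%) | -.062/-.107/-.133 |
| Total × time | interaction | +.018/+.044/+.062 (5%/11%/16%) | -.043/-.067/-.076 |

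A per-person total is constant over visits, so it leaves the within-person contrast alone. It does move the treatment-condition term, which the plan also lists as a primary predictor. In Case A that average effect is (0 - 0.40 - 0.40)/3 = -0.27. By hand, the covariance of the visit mean with the total is 4ρ/3, the variance of the total is 2 + ρ², and the arm difference in the total is -0.8ρ. The shift is therefore (4ρ/3)(0.8ρ)/(2+ρ²) = .046/.119/.163, in line with the simulation. The same shift applies at every visit, so it also produces a baseline difference between arms that does not exist.

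**5. Scale.** The interaction contrast (mean of two later visits minus baseline) has variance .75 + 1 - 2(.5) = .75 per person. With 25 per arm its standard error is √(.75 × 2/25) = 0.245; simulated values were .24 to .25. The non-zero interaction shifts are thus about 0.1 to 0.5 standard errors.

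**6. Cross-check with a different model.** Assignment lowers mid-course severity by a. Severity drives services (slope g) and outcome (slope h). Services lower symptoms by b, and the app raises services directly by c. Then β = hg - b, D = c - ga, and the shift is (hg - b)(ga - c).
- True effect -0.60, a = .6, g = h = .7, b = c = 0: shift .49 × .42 = +.206, giving -0.39.
- No true effect, a = b = 0, g = h = .5, c = .6: shift .25 × (-.6) = -0.15.
- a = c = 0: no shift.

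**The case against.** **Prior trials.** The same section reports that in the primary mentor's earlier work the arms did not differ on ancillary therapies, emergency visits, school counseling or hospitalizations. This is the documents' only evidence on whether the harmful condition arises, and it points against it. Those trials compared other interventions, so it does not settle the matter. If it does carry over, the adjustment corrects no bias and nothing is lost by dropping it.

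**Helpful services.** The illustration in steps 2 to 4 treats services as inert, although they are given in order to help. With h = .6, simulated estimates (unadjusted then adjusted) were -.213 and -.216 for g = .3, b = .2; -.205 and -.219 for g = .3, b = .3; -.198 and -.178 for g = .5, b = .2; and -.182 and -.182 for g = .5, b = .3. So attenuation can be small, absent or slightly reversed. This stands: the percentages above belong to a range that includes zero. It also confirms that the direction cannot be known beforehand.

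**Counseling rule.** Its sessions follow disclosure of substance use, so a path from the trial outcome is not shown for them. That stands, but they still come after randomisation and cannot confound. Reach to adherence depends on how two loose phrases are read.

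**Mediation models.** The single-visit analyses in the statistical section are mediation models ("the effect of treatment condition, mediated by average treatment adherence, on post-treatment psychiatric and psychosocial functioning will be examined"), which condition on adherence by design. The plan does not say the service rule applies to them; the single-visit figures matter there only if it does.

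**Pilot status.** The plan says "this study does not propose to formally assess clinical efficacy or estimates of effect size", and the outcomes chiefly affected are secondary. That limits the weight of the point. The arms will nevertheless be compared on these outcomes, and the results are meant to support a larger application.

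**Conclusion.** The concern holds. Two firm rules place post-randomisation services in the treatment-effect models, the reason given for the main one is mistaken, and nothing in Statistical analyses overrides them. The adjusted coefficient need not be the effect of being assigned the app.

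Size and sign cannot be fixed from the documents. Under the inert-services assumptions the interaction moves by between 0 and 0.13 SD, with the way services enter the model deciding whether it moves at all. That is modest against a standard error of about 0.25 SD. The distortion requires that assignment changes service use and that services are associated with outcome within arms; without both, the expected shift is zero. The point is worth correcting before analysis, but it does not undermine the pilot.

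**What to change.** 1. Delete the two covariate rules (Availability of Other Ancillary Treatments; Limits to Confidentiality) from the main outcome models, and state that they do not apply to the mediation models of post-treatment and 3-month functioning.
2. In Statistical analyses, restrict the open covariate clause, for primary and secondary outcomes alike, to named variables measured before randomisation.
3. Keep the planned by-arm comparison of service use and report it as an outcome.
4. If a services-adjusted model is still wanted, label it an exploratory sensitivity analysis that is not read as the treatment effect, and state whether services enter as a total, per interval or interacted with time.

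The cost is wording only. The same forms and data are collected, and provision of services to participants is unaffected.
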